1.3.7 Rationale for Chronic Oral Levosimendan

The use of chronic oral levosimendan in treatment of PH-HFpEF subjects is based on the following.

- Levosimendan is uniquely enhances myocardial activity through a tripartite mechanism which involves acting as a calcium sensitizer in cardiomyocytes by increasing the sensitivity of troponin C fibers to ionic calcium and as a vasodilator and cytoprotective agent through the opening of adenosine triphosphate (ATP)-dependent potassium channels on vascular smooth muscle cells and in mitochondria.
- Levosimendan enhances CO and systolic and diastolic function, promotes vasodilatation and peripheral perfusion, reduces pulmonary capillary wedge pressure (PCWP), alleviates symptoms of dyspnea and fatigue, and reduces levels of signifier neurohormones such as brain natriuretic peptide (BNP).
- In the Phase 2 HELP Study in PH-HFpEF patients, levosimendan promoted vasodilation and peripheral perfusion, reduced pulmonary capillary wedge pressure (PCWP) pulmonary arterial pressure (PAP) and right atrial pressure (RAP), and enhanced exercise capacity.
- In the Phase 2 HELP Study in PH-HFpEF patients, levosimendan promoted vasodilation and peripheral perfusion, reduced pulmonary capillary wedge pressure (PCWP) pulmonary arterial pressure (PAP) and right atrial pressure (RAP), and enhanced exercise capacity. These positive effects of levosimendan may be due to levosimendan's ability to increase venous capacitance and reduce stressed blood volume (55).
- Oral daily dosing of levosimendan will result in more stable blood levels of the active metabolite OR-1896 which is responsible for the chronic efficacy.
- Similar improvements in cardiovascular hemodynamics have been seen in studies that evaluated oral dosing of levosimendan in HFrEF patients.

- A single dose study comparing levosimendan IV vs Oral Administration was conducted by Harjola et al. This study found that single oral doses of levosimendan (1mg, 2mg, and 4 mg) generally produced similar hemodynamic effects seen with comparable IV bolus doses (56)

[figure not shown]

FIGURE 1. Pulmonary capillary wedge pressure (PCWP) and cardiac output in patients receiving intravenous (n = 12) and oral (n = 10) doses of 1 mg and 4 mg of levosimendan (LS) in 2 different studies. Baseline values and maximum responses are shown (mean \pm SEM). The p-values refer to the difference between maximum response and respective baseline value. NS = not significant.

- A sub-study of the PERSIST trial was conducted (Jalanko et al) evaluated hemodynamic changes seen following chronic daily doses of 1mg and 2mg levosimendan. Favorable changes in PCWP and BNP were observed following 90and 180 days of daily oral administration (57)

[figure not shown]

Figure 2. Change of echocardiographic PCWP from baseline to day 180 in placebo and levosimendan treated patients analysed by repeated measures ANOVA ($p = 0.035$).

Table III. Follow-up.

	Baseline	Day 90	Day 180
PCWP (mmHg)			
Placebo	15.9 (5.7)	16.6 (5.5)	17.3 (5.7)
Levosimendan	18.8 (6.1)	16.4 (6.2)	16.4 (5.4)*
HR (bpm)			
Placebo	74 (14)	72 (10)	72 (11)
Levosimendan	73 (10)	78 (12)	81 (12)
SBP (mmHg)			
Placebo	127 (15)	126 (22)	130 (18)
Levosimendan	121 (15)	129 (14)	127 (19)
LVEDD (mm)			
Placebo	66 (8)	66 (8)	67 (7)
Levosimendan	66 (9)	65 (9)	65 (9)
LVEDV (ml)			
Placebo	188 (63)	189 (59)	197 (64)
Levosimendan	211 (72)	196 (64)	205 (75)
LVEF (%)			
Placebo	25% (8)	28% (10)	25% (10)
Levosimendan	25% (5)	26% (8)	26% (7)

Values presented as mean (\pm SD).

* $p = 0.035$ for difference between groups.

1.3.8 Target Plasma Concentrations of OR-1896 in chronic treatment of PH-HFpEF Patients

Levosimendan represents an active prodrug to the active metabolite OR-1896 with extended pharmacodynamic effects that parallel those of levosimendan. The elimination half-life of levosimendan itself is short (approximately 1 hour), whereas that of the metabolite OR-1896 is long (70-80 hours in heart failure subjects). During a long-term oral dosing of levosimendan with constant daily dose, the OR-1896 plasma levels achieve a steady-state with minimal daily variation.

The chronically active moiety of levosimendan administration is the metabolite OR-1896. Levosimendan is cleared within 5 hours of ending an infusion.

The wide range of OR-1896 concentrations observed in daily oral levosimendan dosing (PERSIST study, see Section 1.3.4) and weekly IV administration (HELP Study, Section 1.3.5) precludes the identification of a specific oral dose to be used in the IV to oral transition. Importantly, the range of OR-1896 plasma concentrations observed in the PERSIST study of class IIIb-IV CHF patients overlap those observed in the HELP Study of PH-HFpEF patients (Figure 3).

[figure not shown]

Figure 3. Comparison of OR-1896 Plasma Concentrations in PERSIST Study of Daily Oral Levosimendan (1mg QD, 1 mg BID) versus the HELP Study of Weekly IV Levosimendan (0.1 ug/kg/min for 24 hrs).

However, only one third of the HELP Study patients were sampled at peak OR-1896 levels, 2-3 days following their previous levosimendan IV dose. The remaining patients were sampled beyond the period of peak OR-1896 concentrations observed in a weekly IV levosimendan regimen. An opportunity to titrate patients to 4 mg total daily dose (1mg QID), as tolerated based on blood pressure and heart rate, will ensure all transitioning patients will achieve adequate steady state levels of OR-1896.

1.3.8.1 IV Levosimendan

OR-1896 concentrations were modeled for the intravenous levosimendan dose regimen of used in LEVO-REP and LION-HEART (0.2µg/kg/min for 6 hrs every two weeks). OR-1896 concentrations displayed average C_{max} and C_{min} values of 1.5 ng/mL and 0.25 ng/mL, respectively, with a C_{avg} of approximately 1.0 ng/mL during each two-week dose interval. The effective target concentrations of OR-1896 were expected to be between 0.5 ng/mL and 2.5 ng/mL in extended intermittent use.

In the HELP Study, PK samples were collected at the final visit. Generally, the samples were collected 2-8 days after completion of the final levosimendan infusion on Week 5. There was a large range of OR-1896 levels (0.347 to 23.8 ng/mL). Some of the variation is associated with the time since completion of the previous levosimendan dose. Patients returning 2-3 days after their dose tended to have higher plasma concentrations of the metabolites. There were several apparent anomalies in levosimendan, OR-1855 and OR-1896 plasma concentrations which have not been explained, despite an internal audit by the laboratory conducting the analyses. There was no identifiable lower or upper limit of OR-1896 that predicts efficacy as measured by hemodynamic or 6MWD.

1.3.8.2 Oral Levosimendan

Orion performed the PERSIST study in 307 CHF patients receiving oral levosimendan at 1mg QD, 1mg BID, or placebo for 6 months. Levosimendan patients demonstrated substantial reductions in NT-proBNP and dose-related improvement in the Minnesota Living with Heart Failure quality of life score (MLHFQOL). The mean (SD) steady state OR-1896 concentrations were 2.7 (SD 2.8) and 4.3 (SD 3.4) ng/mL at 1mg QD and 1mg BID, respectively on Day 30 and remained consistent through the treatment period.

The plot of OR-1896 concentrations in patients receiving oral levosimendan at 1mg QD or 1mg BID in the PERSIST study overlaps the range of OR-1896 concentrations observed in patients receiving weekly intravenous levosimendan at 0.1 µg/kg/min for 24 hours in the HELP Study of PH-HFpEF patients (Figure 3). OR-1896 concentrations in both studies were highly variable.

1.3.8.3 Individualized Oral Dose Regimen

The broad range of observed OR-1896 concentrations in the HELP and PERSIST studies indicates a personalized daily dose may improve individual patient response to levosimendan and its active metabolite OR-1896. The wide range in plasma levels of OR-1896 observed in the HELP and PERSIST studies indicate steady state concentrations from daily dosing will be somewhat independent of body weight or the severity of CHF. The transition from IV to oral levosimendan provides an opportunity for personalized dosing based on patient tolerability.

The step wise increases from 1mg up to 4mg daily levosimendan doses will be based on tolerability of the therapy. Heart rates and blood pressures will be monitored and recorded by the patient each day. Guidance will be provided to ensure measurements are standardized at rest during the same approximate time each day. Investigators will review the heart rate and blood measure measurements to ensure the patient has tolerated their current levosimendan dose and guide the titration (up or down) according to [Attachment 3 Cardiac Event Recommendations and Management](#) and investigator judgment.

2. STUDY OBJECTIVES AND PURPOSE

2.1 Rationale for the Study

The study will evaluate the safety and efficacy of levosimendan in PH-HFpEF subjects. This subject population represents a large and growing group with no established therapies to treat their pulmonary vascular disease (PVD) and right ventricular disease (RVD). Levosimendan and its prolonged active metabolite, OR-1896, have been shown to have favorable hemodynamic effects in subjects with pulmonary hypertension and right heart failure. Clinical studies that have been conducted in subjects with right heart failure and pulmonary hypertension suggest levosimendan may be an effective therapy in treatment of subjects with PH-HFpEF.

2.2 Study Objectives

2.2.1 Primary Objectives

This study will evaluate the safety and tolerability of levosimendan in extended use after completion of the parent study.

2.2.2 Secondary Objectives

The study will evaluate whether the effectiveness of intermittent (weekly) levosimendan and daily oral levosimendan (based on patient transition) is sustained in extended use.

2.3 Study Design

This extension study is designed to investigate the safety and efficacy of extended levosimendan in patients who previously received levosimendan in PH-HFpEF study sponsored by Tenax and may, in the investigator's opinion, derive benefit from continued treatment. Patients will be screened for eligibility at the last visit in the treatment period of the parent study. Eligible patients will be enrolled into the study immediately upon confirmation of eligibility so that levosimendan is not interrupted.

Efficacy assessments (6MWT, Patient global assessment (based on the KCCQ instrument), Physician's Assessment of Functional Class, Clinical Events; Death and hospitalizations) will be performed at 3, 6, 12, 24, 48, and yearly through Follow-up/Termination visit. For patients that transition from IV to oral (Week 0 and 6 or 8), the Time and Events Schedule for oral levosimendan should be followed. Patients will undergo a Follow-Up Visit (at termination) as soon as possible after study drug discontinuation, but within 2 weeks.

For patients that transition to oral levosimendan, the patient should be instructed to monitor their resting heart rate and blood pressure each day prior to the first dose. The patient should use the home monitoring device (provided at the initiation of the initial levosimendan study) to determine their resting heart rate and blood pressure after being seated at rest for at least 5 minutes. The heart rate and blood pressure readings should be recorded in the diary provided as well as the number of capsules the patient has taken each day. The patient should have their diary ready to review with the investigative site in each communication with the site and at office visits.

Patients whose BP falls below the specified range will be queried regarding any symptoms of hypotension which may result in the down titration of the levosimendan dose.

Patients whose heart rate exceeds the specified range will be queried regarding symptoms of worsening heart failure. An excessive heart rate in a patient with no evidence of worsening heart failure, suggests that the increased heart rate is a direct drug effect requiring adown titration of the levosimendan dose.

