7.1.4 IV-Oral Transition Week 6 – Final Visit

During this visit, the following procedures will be performed:

- Vital signs and ECG
- Physical Exam
- Hematology and chemistry blood samples
- Assess adverse events
- Pharmacokinetic sample
- 6MWT
- NYHA Functional Class
- Kansas City Cardiomyopathy Questionnaire (KCCQ)

Once a patient transitions to oral levosimendan, all references in this protocol to the administration of IV levosimendan, will no longer apply for that patient. All study drug and ancillary supplies related to the administration of IV levosimendan will be returned to the central pharmacy for destruction.

7.1.5 IV-Oral Transition Week 8

This visit is only required for patients who titrated (up or down) at the Week 6 visit.

During this visit, the following procedures will be performed:

- Vital signs
- Physical Exam
- Hematology and chemistry blood samples
- Assess adverse events
- Pharmacokinetic sample
- 6MWT
- NYHA Functional Class
- Kansas City Cardiomyopathy Questionnaire (KCCQ)

The Physical Exam, 6MWT, NYHA Functional Class, and KCCQ do not need to be performed for patients who are scheduled for a Week 8 visit, due to either up or down titration of study drug.

Following the Final Evaluation (either Week 6 or Week 8), patients will continue to visit the investigational site at weeks 3, 6, 12, 24, 48, and yearly through the Follow-Up Visit (at termination) and/or Termination visit. These visit windows will be based on the date the patient originally enrolled in the TNX-LVO-05 study. Visits that overlap may be combined into one visit.

Patients unable to return at the scheduled Week 6 or 8 visit, may have their final visit extended.

7.2 Weeks 3, 6, 12, 24, 48, and yearly through the Follow-up and/or Termination

visit (Office Visits)

Visits at Weeks 3, 6, 12, 24, 48, and yearly through the Follow-up and/or Termination visit should be performed within ± 72 hours of the scheduled weekly visit. These visits may be performed at the investigator's office. For any patients who remain on IV levosimendan, the Follow-Up Visit (at termination) will be calculated as the earlier of two years from the subject's date of entry into the TNX-LVO-05 Study or as soon as possible after study discontinuation, but within 1 week.

During this visit, the following procedures will be performed:

- Vital signs
- Physical Exam
- Hematology and chemistry blood samples
- Body Weight
- 6MWT
- Kansas City Cardiomyopathy Questionnaire (KCCQ)

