10.9 Efficacy Analysis

All efficacy endpoints are considered secondary endpoints. Descriptive statistics for efficacy endpoints will be reported at 3, 6, 12, 24, 48 and Follow-Up Visit (at termination) as well as Week 0 and Week 6 (or 8) for IV to oral transition patients.

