2.2 Study Design

2.2.1 Overview

This extension study is designed to investigate the safety and efficacy of extended levosimendan in patients who previously received levosimendan in the Pulmonary Hypertension with Heart Failure and Preserved Left Ventricular Ejection Fraction (PH-HFpEF) study sponsored by Tenax and may, in the investigator's opinion, derive benefit from continued treatment. Patients will be screened for eligibility at the last visit in the treatment period of the parent study. Eligible patients will be enrolled into the study immediately upon confirmation of eligibility so that levosimendan is not interrupted.

Efficacy assessments (Six-minute walk test (6MWT), Patient global assessment (based on the Kansas City Cardiomyopathy Questionnaire (KCCQ) instrument), Physician's Assessment of Functional Class (measured by New York Heart Association (NYHA) functional class assessment), Clinical Events (death and hospitalizations)) will be performed at 3, 6, 12, 24, 48 weeks and yearly through the Follow-up/Termination visit. Patients will undergo a follow-up visit (at termination) as soon as possible after study drug discontinuation, but within one (1) week.

Patients whose blood pressure (BP) falls below the specified range will be queried regarding any symptoms of hypotension which may result in the down titration of the levosimendan dose. Patients whose heart rate exceeds the specified range will be queried regarding symptoms of worsening heart failure. An excessive heart rate in a patient with no evidence of worsening heart failure, suggests that the increased heart rate is a direct drug effect requiring a down titration of the levosimendan dose.

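### Protocol 10.9 leaves the yearly on-drug visits out of the efficacy summaries, so for patients who switch late the only summarised oral value after Week 6/8 is taken after drug stops

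*Protocol*

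**What the plan says.** Protocol 2.2.2 and SAP 2.1.2 make durability of effect the secondary objective; the SAP wording confines it to daily oral drug. The synopsis and Protocol 4.3 keep consenting patients in the study for 3 years after the switch.

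**Assessment.** Protocol 2.3 says efficacy assessments "will be performed at 3, 6, 12, 24, 48, and yearly through Follow-up/Termination visit". The Time and Events Schedule, Protocol 7.2 and SAP 2.3.2 agree that yearly visits are included.

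**Reporting.** Protocol 10.9 says "Descriptive statistics for efficacy endpoints will be reported at 3, 6, 12, 24, 48 and Follow-Up Visit (at termination", and adds "as well as Week 0 and Week 6 (or 8) for IV to oral transition patients". Yearly visits are not in that list. SAP 3.4.2 sends all secondary endpoint measurements to patient-level listings, and the SAP's table list contains no efficacy table.

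**Clock.** For the numbered weeks after the switch, Protocol 7.1.5 says "These visit windows will be based on the date the patient originally enrolled in the TNX-LVO-05 study".

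**Termination visit.** Protocol 2.3 says "Patients will undergo a Follow-Up Visit (at termination) as soon as possible after study drug discontinuation, but within 2 weeks". SAP 2.2.1 says "as soon as possible after study drug discontinuation, but within one (1) week". Protocol 7.2 also has a one-week limit, but only for one group: "For any patients who remain on IV levosimendan, the Follow-Up Visit (at termination) will be calculated as the earlier of two years" from entry, or within a week of discontinuing.

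**ECG.** The Schedule marks ECG at the final parent-study visit, transition Week 0, Week 6 or 8, and the Follow-up Visit. The office/yearly column is blank, and the procedure list in 7.2 has no ECG.

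**The concern.** The visits that can answer the durability question are the yearly ones, when the patient is taking capsules. They are collected but not named for summary. The late time point that is named is, by definition, after drug has stopped. Protocol 1.3.7 attributes the chronic effect to OR-1896, so a 6MWT, KCCQ or NYHA value at that visit is measured at falling exposure. How far exposure has fallen depends on which window a site follows and when the patient comes in. A reader of the summaries could not tell loss of effect on treatment from loss of drug.

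ECG values are part of the primary endpoint. After Week 6/8 the only scheduled ECG falls at this same visit.

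**Working it through.** The plan gives no sample size, power or test on this point (SAP 3.1.5 rules out hypothesis testing), so there is no stated figure to reproduce. The check compares the visit schedule with the reporting list and then computes residual exposure.

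**1. When does Week 48 fall on oral drug?** Let *t* be the study week of oral Week 0. The last transition visit is at *t* + 6, or *t* + 8 if the dose is titrated at Week 6. Week 48 comes later only if
- *t* + 6 < 48, so *t* < 42; or
- *t* + 8 < 48, so *t* < 40.

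From *t* = 42 (or 40) onward, none of Weeks 3-48 follows the transition. In the 10.9 list, only the termination visit is then left.

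**2. How many on-drug yearly visits are collected?** Three years of oral drug is about 156 weeks. The span after the last transition visit is 156 − 6 = 150 or 156 − 8 = 148 weeks. At 52-week spacing, 150/52 = 2.9 and 148/52 = 2.8, so 2 or 3 yearly visits fall inside it. The documents do not define the yearly grid. Placing it at 52, 104, … or at 100, 152, … weeks gives 2 to 3 either way. The number named in 10.9 is 0.

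**3. Residual OR-1896 at the termination visit.** Protocol 1.3.8 puts the parent drug's half-life at about 1 hour, "whereas that of the metabolite OR-1896 is long (70-80 hours in heart failure subjects". Assuming first-order decay from steady state with no further formation, the fraction left is 0.5^(24 × days / half-life):

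| Days since last dose | Half-life 70 h | Half-life 80 h |
|---|---|---|
| 1 | 0.5^0.343 = 78.8% | 0.5^0.300 = 81.2% |
| 7 | 0.5^2.4 = 18.9% | 0.5^2.1 = 23.3% |
| 14 | 0.5^4.8 = 3.6% | 0.5^4.2 = 5.4% |

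Between the outer limits of the two windows, residual metabolite differs by 2^2.1 = 4.3-fold to 2^2.4 = 5.3-fold.

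**4. Can the gap be seen in the data?** Protocol 3.4 requires the stop date on the eCRF. SAP 3.3.5, however, in some cases imputes the last oral dose as the day before the follow-up visit. For those patients a gap computed from the imputed date is always one day, whatever happened.

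**5. Scheduled on-drug ECGs after Week 6/8:** 0 in the Schedule.

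**The case against.** Several points on the other side stand, and they limit the finding.

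- A reader might infer that the termination value is the only late efficacy result reported for oral patients. It is not. Every yearly value goes into SAP Listings 16.2.6.1 to 16.2.6.3, and patients who switch before about study week 40-42 keep a Week 48 on oral drug. The documents give no distribution of switch dates, so the number affected is unknown. Protocol 7.2 does provide for a Week 48 or yearly visit landing near the transition visits, so late switching was foreseen.
- A reader might infer that long-term safety on drug cannot be assessed. The documents do not support that. Adverse events are collected throughout, vital signs and local labs are scheduled at the office visits, and Attachment 3 calls for an ECG when a validated heart rate exceeds 120 without symptoms. The gap is in scheduled ECGs only.
- It is tempting to scale the 29.3 m walk-distance difference (1.3.5) or the 7-8 bpm heart-rate rise (1.3.4) by the residual fractions. Protocol 1.3.8.1 reports no OR-1896 limit that predicted haemodynamic or 6MWD response. Its final-visit samples were themselves generally taken 2-8 days after the infusion. Protocol 1.3.8 puts the metabolite peak 2-3 days after an IV dose, so simple decay may understate what remains. No loss in metres or bpm should be quoted.
- Both documents ask for the visit as soon as possible. A day-1 visit would be close to on-drug exposure, but nothing requires day 1.
- SAP section 4 cites protocol v5.0, while the protocol supplied is v4.1. A later version may have changed the window or 10.9.

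None of this restores the yearly visits to the summaries. Listings are not the descriptive statistics that 10.9 promises.

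**Conclusion.** The point holds as a reporting gap with a conflicting visit window. For patients whose oral Week 0 falls at about study week 40-42 or later, 10.9 summarises no on-drug efficacy value after Week 6/8, although 2-3 yearly visits are collected in a full 3-year oral course. The late value it does name is off drug, within 2 weeks (Protocol 2.3) or 1 week (SAP 2.2.1). Residual OR-1896 at those limits would be 4-5% and 19-23%, against about 80% on day 1. The exposure figures rest on the 70-80 h half-life and simple first-order decay. They describe concentration only, because the documents do not establish what residual concentration means for 6MWD or heart rate. No on-drug ECG is scheduled after Week 6/8. The data needed for the objective are collected, so this should be corrected, but it does not undermine the study.

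**What to change.** 1. Add the yearly visits to the efficacy time points in Protocol 10.9, and add an efficacy summary to the SAP that shows oral-period values by time since oral start. SAP 3.1.1 counts days from the first dose by either route, so this needs one derived variable and a few tables, with no new data.
2. Reconcile the 2-week window in Protocol 2.3 with the 1-week window in SAP 2.2.1, and state to which patients it applies, given the IV-only limit in 7.2.
3. Report each termination value with days since the recorded, not imputed, last dose. Do not pool off-drug values with on-treatment values.
4. For patients who reach the planned end of treatment, perform the existing termination ECG and efficacy assessments before the last dose where feasible. This needs no extra visit.

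Items 1 to 3 cost wording and programming. Item 4 gives up some off-drug observations, though SAEs are still collected for 30 days after the last dose (9.2.4). It supplies one on-drug ECG at the end of treatment and does not fill the years between, which the study report should say.
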